### 11.4.4 Reporting of SAEs

#### SAE Reporting to the Sponsor via an Electronic Data Collection Tool

- The primary mechanism for reporting an SAE to the sponsor will be the electronic data collection tool.
- If the electronic system is unavailable, then the site will use the paper SAE data transmission (see next section) to report the event within 24 hours.
- The site will enter the SAE data into the electronic system as soon as it becomes available.

---

- After the study is completed at a given site, the electronic data collection tool will be taken off-line to prevent the entry of new data or changes to existing data.
- If a site receives a report of a new SAE from a study participant or receives updated data on a previously reported SAE after the electronic data collection tool has been taken off-line, then the site can report this information on a paper SAE form (see next section) or to the sponsor's Medical Monitor (Study Medical Expert) by telephone.
- Contacts for SAE reporting can be found in the Investigator Site File.

---

#### **SAE Reporting to the Sponsor via Paper Data Collection Tool**

- Facsimile transmission of the SAE paper CRF is the preferred method to transmit this information to the sponsor's Medical Monitor (Study Medical Expert).
- In rare circumstances and if email transmission is not feasible, notification by telephone is acceptable with a copy of the SAE data collection tool sent by overnight mail or courier service.
- Initial notification via telephone does not replace the need for the investigator to complete and sign the SAE data collection tool within the designated reporting time frames.
- Contacts for SAE reporting can be found in the Investigator Site File.

---

**11.5 Appendix 5: Medical Device AEs, SAEs, and Device Deficiencies:  
Definitions and Procedures for Recording, Evaluating, Follow-up, and  
Reporting**

- Both the investigator and the sponsor will comply with all local reporting requirements for medical devices.
- The detection and documentation procedures described in this protocol apply to all sponsor medical devices provided for use in the study. See [Section 6.1.1](#) for the list of sponsor medical devices.

### **11.5.1      Definition of Medical Device AE**

---

#### **Medical Device AE**

- An AE is any untoward medical occurrence in a clinical study participant, users, or other persons, temporally associated with the use of study intervention, whether or not considered related to the medical device provided by the study sponsor. An AE can therefore be any unfavorable and unintended sign (including an abnormal laboratory finding), symptom, or disease (new or exacerbated) temporally associated with the use of the medical device. This definition includes events related to the investigational medical device and events related to the procedures involved.

---

### **11.5.2      Definition of Medical Device SAE**

---

#### **A medical device SAE is any SAE that:**

- a. Led to death
- b. Led to serious deterioration in the health of the participant, that either resulted in:
  - A life-threatening illness or injury. The term 'life-threatening' in the definition of 'serious' refers to an event in which the participant was at risk of death at the time of the event. It does not refer to an event, which hypothetically might have caused death, if it were more severe.
  - A permanent impairment of a body structure or a body function.
  - Inpatient or prolonged hospitalization, planned hospitalization for a pre-existing condition, or a procedure required by the protocol, without serious deterioration in health, is **not** considered an SAE.
  - Medical or surgical intervention to prevent life-threatening illness or injury or permanent impairment to a body structure or a body function.
  - Chronic disease (EU Medical Device Regulation 2017/745).
- c. Led to fetal distress, fetal death or a congenital abnormality or birth defect

---

### **11.5.3      Definition of Device Deficiency**

---

#### **Device Deficiency Definition**

- A device deficiency is an inadequacy of a medical device with respect to its identity, quality, durability, reliability, safety, or performance. Device deficiencies include malfunctions, use errors, and inadequacy of the information supplied by the manufacturer.

---

### **11.5.4      Recording and Follow-up of Medical Device AEs/SAEs/Device Deficiencies**

---

#### **Assessment of Intensity**

---

The investigator will make an assessment of intensity for each AE/SAE/device deficiency reported during the study and assign it to one of the following categories:

- Mild: Asymptomatic or mild symptoms; clinical or diagnostic observations only; intervention not indicated.
- Moderate: Minimal, local or noninvasive intervention indicated; limiting age-appropriate instrumental Activities of Daily Living (ADL). Instrumental ADL refers to preparing meals, shopping for groceries or clothes, using the telephone, managing money, etc.
- Severe: Severe or medically significant but not immediately life-threatening; hospitalization or prolongation of hospitalization indicated; disabling, limiting self-care ADL. Self-care ADL refers to bathing, dressing and undressing, feeding self, using the toilet, taking medications, and not bedridden.

### **Assessment of Causality**

The investigator will provide a preliminary assessment of the relationship between the event and the medical devices listed in [Section 6.1.1](#).

### **Follow-up of AE/SAE/Device Deficiency**

- The investigator is obligated to perform or arrange for the conduct of supplemental measurements and/or evaluations as medically indicated or as requested by the sponsor to elucidate the nature and/or causality of the AE/SAE/device deficiency as fully as possible. This may include additional laboratory tests or investigations, histopathological examinations, or consultation with other HCPs.
- If a participant dies during participation in the study or during a recognized follow-up period, the investigator will provide the sponsor with a copy of any postmortem findings including histopathology.
- New or updated information will be recorded in the originally completed form.

The investigator will submit any updated SAE data to the sponsor within 24 hours of receipt of the information.

---

### **11.5.5 Reporting of AEs/SAEs Related to the Device**

- For any SAE that was assessed as device-related: the investigator should manually complete the Medical Device Incident form and electronically complete the complementary SAE page in RAVE. The Medical Device Incident form will be sent to the sponsor via email at [[contact]](mailto:[contact]) within 24 hours.
- For any AE that was assessed as device-related: the investigator should manually complete the Medical Device Incident form and electronically complete the complementary AE page in RAVE. The Medical Device Incident form will be sent to the sponsor via email at [[contact]](mailto:[contact]) within 24 hours.

---

---

- If the device deficiencies could potentially lead to the death or serious deterioration of health (serious injury) of the study participant or others (e.g. staff), manually complete the Medical Device Incident form only and send it to the sponsor via email at [[contact]](mailto:[contact]) within 24 hours.  
For any AE or SAE that occurred in a person other than the study participant, the investigator should manually complete the Medical Device Incident form only and send it to the sponsor via email at [[contact]](mailto:[contact]) within 24 hours.

---

## 11.6 Appendix 6: Contraceptive Guidance and Collection of Pregnancy Information

### Definitions:

#### Woman of Childbearing Potential (WOCBP)

A woman is considered fertile following menarche and until becoming postmenopausal unless permanently sterile (see below).

If fertility is unclear (e.g. amenorrhea in adolescents or athletes) and a menstrual cycle cannot be confirmed before first dose of study intervention, additional evaluation should be considered.

Women in the following categories are not considered WOCBP

1. Premenarchal
2. Premenopausal female with 1 of the following:

- Documented hysterectomy
- Documented bilateral salpingectomy
- Documented bilateral oophorectomy

For individuals with permanent infertility due to an alternate medical cause other than the above, (e.g. mullerian agenesis, androgen insensitivity), investigator discretion should be applied to determine study entry.

Note: Documentation can come from the site personnel's: review of the participant's medical records, medical examination, or medical history interview.

3. Postmenopausal female

- A postmenopausal state is defined as no menses for 12 months without an alternative medical cause.
  - A high FSH level in the postmenopausal range may be used to confirm a postmenopausal state in women not using hormonal contraception or HRT. However, in the absence of 12 months of amenorrhea, confirmation with more than one FSH measurement is required.
- Females on HRT and whose menopausal status is in doubt will be required to use one of the non-estrogen hormonal highly effective contraception methods if they wish to continue their HRT during the study. Otherwise, they must discontinue HRT to allow confirmation of postmenopausal status before study enrollment.

### Contraception Guidance:

WOCBP can only be included in the study if a pregnancy test is negative at the screening visit and if they agree to use adequate contraception during the study period until 8 weeks after last study intervention. Adequate contraception is defined as any combination of at least 2 effective methods of birth control, of which at least 1 is a physical barrier (e.g. condoms with hormonal contraception or implants or combined oral contraceptives, certain intrauterine devices).

For nulliparous adolescent participants, LARC methods are considered first-line options.

**Collection of pregnancy information for female participants who become pregnant:**

- The investigator will collect pregnancy information on any female participant who becomes pregnant while participating in this study. The initial information will be recorded on the appropriate form and submitted to the sponsor within 24 hours of learning of a participant's pregnancy.
- The participant will be followed to determine the outcome of the pregnancy. The investigator will collect follow-up information on the participant and the neonate and the information will be forwarded to the sponsor. Generally, follow-up will not be required for longer than 6 to 8 weeks beyond the estimated delivery date. Any termination of pregnancy will be reported, regardless of fetal status (presence or absence of anomalies) or indication for the procedure.
- While pregnancy itself is not considered to be an AE or serious AE (SAE), any pregnancy complication or elective termination of a pregnancy for medical reasons will be reported as an AE or SAE.
- A spontaneous abortion (occurring at < 22 weeks' gestational age) or still birth (occurring at > 22 weeks' gestational age) is always considered to be an SAE and will be reported as such.
- Any post-study pregnancy-related SAE considered reasonably related to the study intervention by the investigator will be reported to the sponsor as described in [Section 8.4.4](#). While the investigator is not obligated to actively seek this information in former study participants, he or she may learn of an SAE through spontaneous reporting.
- Any female participant who becomes pregnant while participating in the study will discontinue study intervention and be withdrawn from the study after completing early withdrawal visit.

## 11.7 Appendix 7: Visit Description

### 11.7.1 Visit 1 – Screening (Up to 30 Days Prior to Baseline)

Screening may take place over multiple site visits. At the screening visit, the following procedures and assessments will be performed:

- Obtain signed informed consent (and assent) from participant and parent(s) or legal guardian(s), as necessary.  
Note: No screening procedures should be performed unless written informed consent (and assent) has been obtained.
- Allocation of a unique participant number.
- Review of eligibility requirements; no participant should receive study intervention unless all inclusion and no exclusion criteria are met as listed in [Section 5.1](#) and [5.2](#). Confirmation of selection criteria may be based on medical records for some conditions, but laboratory test results must be available for the listed items to confirm eligibility.
- Collect demographic data (age, sex, race, ethnicity) as well as blood type and weight.
- Collect information on previous hemophilia treatment.
- Obtain a complete medical and surgical history (general, disease, family history of hemophilia, and history of inhibitor development).
  - Specific information on history of hemophilia (date of diagnosis, start of prophylaxis, prior and current FVIII products, estimated number of ED, type of human coagulation FVIII gene mutation (from history), family history, FVIII level and type of assay, family and personal history of past inhibitor formation (including date of inhibitor testing, whether immune tolerance induction was performed, and recovery and half-life data, if available; [Section 1.3](#)), current treatment product and regimen, number and type of bleeds in the last 12 months, and presence and location of target joints). If available, data on prior pharmacokinetics with the participants' previous FVIII product will be collected (e.g. concentration timepoints and half-life).
- Collect information on previous medication (medication history, including substance usage).
- Concomitant medication review.
- AE/SAE review  
Note: Only events which are related to protocol-required study procedures will be recorded from the signing of the ICF.
- Blood samples for the following (see details in [Table 11-1](#)):
  - Pregnancy test (female participants)
  - Laboratory evaluation (platelets and von Willebrand factor (vWF): antigen).  
Note: If available in the medical records, vWF antigen testing should have been performed within 12 months prior to enrollment
  - HIV screening, if not available in medical records

- CD 4+ cell count (only if participant is HIV positive and if not available in medical records)
- Immunogenicity testing (human recombinant factor VIII [rFVIII] inhibitor)
- Training on use of eDiary and confirm participant access to eDiary

### 11.7.2 Visit 2 – Baseline (Day 1)

This visit will serve as the Baseline Visit; it will include the first administration of study intervention. The Baseline Visit should take place within 30 days after the screening visit.

This visit should start with the following assessments:

- Confirmation of eligibility including check of laboratory test results

Note: Participants must have negative results from the local laboratory for inhibitory antibodies against FVIII (< 0.6 BU/mL determined with the Bethesda assay as per local clinical practice)

Thereafter, the following procedures and assessments will be performed and data recorded:

- Physical examination including height and weight
- Collect information on physical activity level (medium/high [contact sports]; low [non-contact sports]; sedentary). Please see [Table 4–1](#) and [Figure 4–1](#).
- Assessment of joint status
- Concomitant medication review
- AE/SAE/AESI review
- Administration and completion of PRO questionnaires (Haemophilia Quality of Life [Haem-A-QoL or Haemo-QoL], EuroQoL 5 Dimensions [EQ-5D-5L], Treatment Satisfaction Questionnaire for Medication [TSQM], and Work Productivity and Activity Impairment [WPAI] questionnaires)
- Blood sample collection **before** administration of study intervention for incremental recovery of Jivi (FVIII levels)
- Infusion of Jivi at study site
- Procedures and sample collection **after** administration of study intervention for incremental recovery of Jivi (15 to 30 minutes after end of infusion and at a minimum of 4 hours after end of infusion to assess FVIII levels; see [Section 8.5.1](#))
  - In case of any infusion-related AE, vital signs will be collected.
- Pregnancy test for female participants if visit occurs >14 days after last menstrual period
- Bleeding risk score calculation and prophylaxis regimen selection
- Dispense study intervention for home infusions
- Instruction on the treatment regimen to be administered to the participant
- Check of eDiary entries and bleeding history

Begin regular monthly contact between participant and the site to check eDiary documentation and review AEs and concomitant medication use until the EOS/Early Withdrawal.

### **11.7.3 Visit 3, 4 – (Months 1, 2)**

This visit should take place via telephone.

- Dose regimen adjustment according to score. At Visit 3 for medium risk participants and Visits 3 and 4 for low risk participants
- At home infusion of Jivi
- Concomitant medication review
- AE/SAE/AESI review
- Check of eDiary entries and bleeding history

### **11.7.4 Visit 5 – (Month 3)**

This in-person visit should take place 72 hours after the last infusion of Jivi.

- Collect information on physical activity level (medium/high [contact sports]; low [non-contact sports]; sedentary)
- Measurement of weight
- Blood sample collection 3 days after previous dose for all participants: FVIII (Jivi) levels for all participants for Web-accessible Population Pharmacokinetic Service-Hemophilia (WAPPS-Hemo) PK analysis. For participants on the 2x/week regimen, collected samples will also serve as a trough level measurement.
- If the PI feels the baseline peak FVIII level at 15-30 minutes or 4-8 hours post-infusion at Visit 2 does not seem to be appropriate for the dose infused, then the levels should be repeated at Visit 5 and the results also uploaded to WAPPS-Hemo. For those patients who do not have appropriate FVIII levels at either Visit 2 or Visit 5, the levels should be repeated at Visit 6.
- Pregnancy test (female participants)
- Infusion of Jivi at study site (not mandatory)
- Concomitant medication review
- AE/SAE review
- Administration and completion of PRO questionnaire (EQ-5D-5L only)
- Return used vials, and dispense remainder of study intervention
- Check of eDiary entries and bleeding history

### **11.7.5 Visit 6 – (Month 6, End of Study/Early Withdrawal)**

This in-person visit should take place in alignment with the weekly prophylaxis regimen (i.e. as close as possible to the participant's next infusion) as follows: on Day 4 for participants on the 2x/week regimen, on Day 5 for participants on the Q5D regimen, and on Day 7 for participants on less frequent regimens (e.g. Q7D).

The following procedures and assessments will be performed in participants at the EOS visit or at the time of premature termination:

- Concomitant medication review
- AE/SAE/AESI review
- Physical examination including height and weight
- Assessment of joint status
- Collect information on physical activity level (medium/high [contact sports]; low [non-contact sports]; sedentary)
- Blood sample collection **before** administration of study intervention: FVIII (Jivi) trough levels
  - Sample collection on Day 4 for participants on the 2x/week regimen, on Day 5 for participants on the Q5D regimen, and on Day 7 for participants on less frequent regimens (e.g. Q7D)
- Pregnancy test (female participants)
- In-hospital infusion of Jivi
- If the PI feels the baseline peak FVIII level at 15-30 minutes or 4-8 hours post-infusion at Visit 2 does not seem to be appropriate for the dose infused, then the levels should be repeated at Visit 5 and the results also uploaded to WAPPS-Hemo. For those patients who do not have appropriate FVIII levels at either Visit 2 or Visit 5, the levels should be repeated at Visit 6.
- Administration and completion of PROs (Haem-A-QoL or Haemo-QoL, EQ-5D-5L, TSQM, WPAI, and Patient's Global Impression of Change [PGI-C])
- Return used and unused vials
- Check of eDiary entries and bleeding history

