g If the investigator feels the baseline peak FVIII level at 15-30 minutes or 4-8 hours post-infusion at Visit 2 does not seem to be appropriate for the dose infused, then, if possible, the levels should be repeated at Visit 5 and the results also uploaded to WAPPS-Hemo. For those patients who do not have appropriate FVIII levels at either Visit 2 or Visit 5, the levels should be repeated at Visit 6.

h WAPPS-Hemo data entry should include FVIII levels measured pre-dose, post-infusion, hour 4-8 at Baseline (Day 1) and Month 3 (Visit 5; 72 hours after the last Jivi infusion).

i von Willebrand factor levels should be recorded within 12 months of screening. Please refer to [Section 8.3.4](#) for timing of von Willebrand factor blood draw.

j At Month 3 (72 hours after the previous infusion for all subjects). Post-infusion FVIII levels will be measured for all participants and included in the WAPPS-Hemo analysis.

k Only (S)AEs which are related to protocol-required study procedures will be recorded from the signing of the consent form until the start of study intervention.

l The first Jivi dose will be administered at the clinic at Baseline (Day 1) and may be administered at the clinic at Month 3 (Visit 5) and Month 6 (EOS/Early withdrawal; as long as the infusion does not occur before blood sampling). All other doses will be self-administered at home.

m In case of any infusion-related AE at a site visit, vital signs will be collected.

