### 8.3.1 Measurements of Immunogenicity

All participants will be tested for inhibitors to FVIII according to the Bethesda assay as per local clinical practice. A positive inhibitor test is defined with a threshold of  $\geq 0.6$  BU/mL. Repeat testing should be obtained within 1 to 2 weeks of initial identification of a positive result. Only after confirmation of a second positive result does the inhibitor have to be reported as a SAE.

A low post-infusion FVIII level in the absence of detectable FVIII inhibitors indicates that loss of drug effect is likely due to anti-PEG antibodies. Jivi should be discontinued and participants switched to a previously effective FVIII product (refer to [Section 8.4.7](#) as this qualifies for an AESI-Loss of Efficacy [LoE]).

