#### **8.4.5 Pregnancy**

- Details of all pregnancies in female participants will be collected after the start of study intervention and until 8 weeks after last dose of study intervention.

- If a pregnancy is reported, the investigator will record pregnancy information on the appropriate form and submit it to the sponsor within 24 hours of learning of the female participant pregnancy.
- While the pregnancy itself is not considered to be an AE or SAE, any pregnancy complication or elective termination of a pregnancy for medical reasons will be reported as an AE or SAE.
- Abnormal pregnancy outcomes (e.g. spontaneous abortion, fetal death, stillbirth, congenital anomalies, ectopic pregnancy) are considered SAEs, and will be reported as such.
- The participant will be followed to determine the outcome of the pregnancy. The investigator will collect follow-up information on the participant and the neonate and the information will be forwarded to the sponsor.
- Any post-study pregnancy-related SAE considered reasonably related to the study intervention by the investigator will be reported to the sponsor as described in [Section 8.4.4](#). While the investigator is not obligated to actively seek this information in former study participants, he/she may learn of an SAE through spontaneous reporting.
- Any female participant who becomes pregnant while participating in the study will discontinue study intervention and be withdrawn from the study after completing the early withdrawal visit.

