#### **8.4.7 Events of Special Interest**

Hypersensitivity reactions, including severe allergic reactions (which can progress to anaphylaxis), chest or throat tightness, dizziness, mild hypotension, and nausea, are known and listed adverse drug reactions for FVIII products and have been reported with use of Jivi. Loss of efficacy of the drug product has also been reported in children < 6 years of age and may be associated with the development of antibodies to PEG. Loss of efficacy can present as bleeding and must be confirmed by low recovery or post-infusion FVIII level, and a negative FVIII inhibitor test. A low recovery or no detectable FVIII post-infusion in a participant with a hypersensitivity reaction in the presence of PEG IgM antibodies is considered LoE even in the absence of a bleeding event. All such reported events (hypersensitivity and LoE) occurred early in treatment (within the first 4 EDs).

Hypersensitivity reactions and LoE are defined in this study as AESIs and must be reported within 24 hours of the investigator's awareness. The LoE must be confirmed by an abnormal low recovery after the infusion of Jivi.

In the event of reported LoE of the study intervention, the following is to be done:

1. Schedule a visit within 4 days of the reported event.
2. Obtain 2 pre-infusion blood/plasma samples for FVIII levels and FVIII inhibitor (for local laboratory).
3. Administer BAY 94-9027 (use current prophylaxis dose [IU/kg]).
4. Obtain one post-infusion blood/plasma samples (for local laboratory) for FVIII levels (15-30 minutes post-infusion).

Non-serious hypersensitivity events should not automatically be upgraded by the reporting investigator to serious.

If hypersensitivity reactions occur, immediately discontinue study intervention administration and initiate appropriate treatment. Please refer to the approved prescribing information.

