#### 4.5.2 Adverse Events

Adverse events will be reported using the latest version of the Medical Dictionary for Regulatory Affairs (MedDRA).

All AEs, SAEs, and AESIs will be collected from Baseline until the end of the Safety Follow-up Visit at the time points specified in the protocol schedule of activities (SoA). Only (S)AEs which are related to protocol-required study procedures will be recorded from the signing of the consent form until the start of study intervention. Adverse events or SAEs will be considered to be treatment-emergent (TEAEs or TE SAEs) if they have started or worsened after first administration of study intervention and not later than 7 days after the last infusion of Jivi.

The AE assessments recorded on the eCRF include SAE (yes/no) and SAE criteria, AESI (yes/no), reasonable causal relationship to Jivi (yes/no), reasonable causal relationship to protocol-required procedure (yes/no), medical device AE or deficiency (yes/no), intensity (mild/ moderate/ severe), action taken with the study intervention (drug withdrawn/ drug interrupted/ dose reduced/ dose not changed/ dose increased/ not applicable/ unknown), remedial drug therapy (yes/no), other actions or treatments of AE, and outcome. The AESIs are hypersensitivity and loss of efficacy (LoE).

An overall summary table of TEAEs will be presented to include all participants and stratified by subgroup of history of FVIII inhibitors. The Overall summary will include number and percentage of participants experiencing AEs in the following categories:

- Any TEAE
- Any TEAE by maximum intensity
- Any study intervention-related TEAE
- Any study procedure-related TEAE
- Any medical device-related TEAE
- Any medical device deficiency
- Any TEAE leading to discontinuation of the study intervention
- Any TEAE of Special Interest (TE AESI), including SAE/AE
- Any study intervention-related TE AESI, including SAE/AE
- Any TE SAE
- Any study intervention-related TE SAE
- Any study procedure-related TE SAE
- Any medical device-related SAE
- Any TE SAE leading to discontinuation of study intervention
- Any TEAE with outcome death

An overall summary of pre-treatment AEs will include number and percentage of participants experiencing pre-treatment AEs in the following categories:

- Any AE with causal relationship to protocol-required study procedures
- Any SAE with causal relationship to protocol-required study procedures

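### The Visit 6 list in Protocol 11.7.5 includes a Jivi infusion without exception at premature termination, which is not reconciled with the SoA or with the sections that stop Jivi

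*Protocol*

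**What the plan says.** Protocol 11.7.5 (Visit 6) introduces a single list: "The following procedures and assessments will be performed in participants at the EOS visit or at the time of premature termination". The list contains "In-hospital infusion of Jivi", with no qualifier and no exception by reason for termination. In 11.7.4 the corresponding Visit 5 item is marked as not mandatory. SoA footnote l (section 1.3) says that, after the first dose, Jivi "may be administered at the clinic at Month 3 (Visit 5) and Month 6", and it names early withdrawal alongside EOS.

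Section 7.1 says that a participant who permanently discontinues study intervention leaves the study and has an EOS visit. Section 7.2 asks for an early withdrawal visit where possible.

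The sections that stop Jivi are:

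- **8.3.1, low post-infusion FVIII without an inhibitor:** "Jivi should be discontinued and participants switched to a previously effective FVIII product".
- **8.4.7, last paragraph:** "If hypersensitivity reactions occur, immediately discontinue study intervention administration and initiate appropriate treatment".
- **8.4.5, pregnancy:** "Any female participant who becomes pregnant while participating in the study will discontinue study intervention". The same sentence then withdraws her after the early withdrawal visit.

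Step 3 of the loss-of-efficacy work-up in 8.4.7 reads "Administer BAY 94-9027 (use current prophylaxis dose [IU/kg".

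SAP 4.5.2 counts an event as treatment-emergent if it starts or worsens after the first dose and "not later than 7 days after the last infusion of Jivi". Protocol 11.7.6 sets Visit 7 at 7 to 14 days after the last dose.

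**The concern.** A participant can be told to stop Jivi by one section, sent to the EOS or early withdrawal visit by another, and there meet a list that includes a further infusion. Section 8 names Appendix 7 as the visit description and allows no waivers or exemptions. On the text alone, a site that omits the infusion departs from 11.7.5, and a site that gives it departs from 8.3.1 or 8.4.7.

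The first thing at stake is participant safety: study drug could be given to someone withdrawn from it for a safety reason. The second is uniformity of the safety data. An infusion at that visit becomes the last infusion, so follow-up and classification dates would depend on which passage the site followed.

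**Working it through.** The plan states no figure on this point. The check is a comparison of passages followed by date arithmetic.

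**Step 1: is the infusion required, optional or excluded after a stop?**

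| Source | Instruction on an infusion | Exception for those who stopped Jivi? |
|---|---|---|
| 11.7.5, Visit 6 list | Listed, under wording that the items will be performed | None |
| 11.7.4, Visit 5 list | Marked not mandatory | Not addressed |
| SoA footnote l | Permitted at Month 6 or early withdrawal, not before blood sampling | None |
| 7.1 | EOS visit after permanent discontinuation | Silent on the infusion |
| 8.3.1 | Jivi stopped for loss of effect | Silent on the visit |
| 8.4.7, last paragraph | Administration stopped for hypersensitivity | Silent on the visit |
| 8.4.5 | Jivi stopped for pregnancy, early withdrawal visit completed | Silent on the infusion |

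Appendix 7 and the SoA disagree on whether the infusion is obligatory, and neither excludes it for a participant who has stopped. Sections 8.3.1 and 8.4.7 do not mention the visit themselves. It is 7.1 that takes those participants there. For pregnancy the route is explicit in 8.4.5.

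**Step 2: section 8.4.7 on its own.** It treats low recovery in a participant with a hypersensitivity reaction and PEG IgM antibodies as loss of efficacy even without a bleed. The loss-of-efficacy steps include an infusion, while the last paragraph stops administration for hypersensitivity. The two instructions meet only where both conditions are present.

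**Step 3: effect on dates.** Let Jivi stop on day D and let an infusion be given at a withdrawal visit on day D + k. The documents do not give k; I assume 1 to 14 days.

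- Treatment-emergent cut-off = last infusion + 7 (SAP 4.5.2)
- Visit 7 = last dose + 7 to 14 (Protocol 11.7.6)
- End of pregnancy collection = last dose + 8 weeks = last dose + 56 (Protocol 8.4.5)

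| Case | Treatment-emergent cut-off | Visit 7 | Pregnancy collection ends |
|---|---|---|---|
| No infusion at the visit | D+7 | D+7 to D+14 | D+56 |
| k = 1 | D+8 | D+8 to D+15 | D+57 |
| k = 10 | D+17 | D+17 to D+24 | D+66 |
| k = 14 | D+21 | D+21 to D+28 | D+70 |

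Every anchor moves by exactly k days. Events starting on D+8 to D+7+k change from post-treatment to treatment-emergent. With assumed dates D = 60 and k = 14, the visit is on Day 74. The cut-off moves from 60 + 7 = Day 67 to 74 + 7 = Day 81, and Visit 7 from Days 67–74 to Days 81–88.

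**Step 4: primary endpoint.** SAP 4.1.1.1 and 4.1.1.4 define the intervention period as 1 + Visit 6/EOS date − Visit 2 date, and frequency is computed from prescribed doses. Whether an infusion is given at the visit enters neither denominator.

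**The case against.** The best reply is that the protocol as a whole does not require this infusion. Sections 7.1 and 7.2 point those who stop to the SoA for what to collect, and footnote l there makes the dose optional. Visit 6 is also timed close to the next scheduled infusion, which presupposes ongoing prophylaxis, and investigators could be expected to read a specific stop instruction ahead of a general checklist line. This stands against any claim that every stopper must, or would, be infused. It does not remove the discrepancy, because footnote l covers early withdrawal without exception and section 8 gives Appendix 7 standing alongside the SoA.

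Several narrower objections also stand:

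- The pregnancy sentence can be read as stopping Jivi only after the early withdrawal visit, so that limb is ambiguous.
- For suspected, unconfirmed loss of efficacy, an infusion is part of the work-up in 8.4.7. A reader might infer that the section contradicts itself for all loss of efficacy, but the text supports this only where hypersensitivity coexists. Even there, the stop could be read as referring to the infusion in progress.
- Cases should be few. Section 7.1 calls permanent discontinuation rare, section 2.3 reports no new or confirmed inhibitors in the clinical studies and places the anti-PEG response mainly in children under 6, and this study enrols about 20–25 participants aged 12 or over.

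A reader might also infer that the SAP window is defective and should be tied to the last infusion before the decision to stop. The documents do not support that. A participant infused at the withdrawal visit is truly exposed, and the current rule is clear. On the dates in Step 3, a reaction on Day 74 to an infusion that day would fall after Day 67 and be classed as post-treatment, which hides the event of most interest.

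**Conclusion.** The concern holds as an internal inconsistency. Section 11.7.5 lists a Jivi infusion without exception at premature termination. The SoA makes it optional, and sections 8.3.1, 8.4.7 and (with ambiguous timing) 8.4.5 stop Jivi for participants whom 7.1 or 8.4.5 sends to that visit. A site following the list could infuse someone withdrawn for safety; the text does not show that any site would. The overlap within 8.4.7 is a secondary point.

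If an infusion is given, the treatment-emergent cut-off and the Visit 7 window shift by k days, that is 1 to 14 days under the assumed range. If none is given, nothing shifts. Events outside the window are still reported, in the post-treatment tables and flagged listings of SAP 4.5.2. The primary endpoint denominators are unaffected. The number of participants concerned cannot be derived from the documents and is probably small, but the conflict bears on safety and is cheap to remove. I take no view on which clinical instruction is right.

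**What to change.** - **Protocol 11.7.5:** separate the procedures for a scheduled EOS visit from those for premature termination.
- **Protocol 11.7.5, SoA footnote l, 7.1, 8.3.1, 8.4.5 and 8.4.7:** reconcile the infusion line across these places so that together they give one instruction for each reason for stopping. Include step 3 of 8.4.7 against its last paragraph, and the timing in the pregnancy sentence. The sponsor's medical lead decides which instruction holds.
- **SAP 4.5.2:** keep the treatment-emergent window on the actual last infusion. At most, add a listing flag for any infusion given only at a withdrawal visit, so that a shifted window can be recognised.

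The cost is wording in one appendix list and one footnote, and in up to four protocol sections, at the next amendment, plus an optional SAP line for the flag. No new visit, sample or procedure is needed.
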